2. LAY SUMMARY

Background

Chiari 1 malformation (CM1) is a structural abnormality of the hindbrain characterised by herniation of the cerebellar tonsils through the foramen magnum. The investigation and management of CM1 remains contentious since there are currently no UK guidelines for clinicians. Practice varies widely between neurosurgical units and individual surgeons, but there is no robust evidence to bring consensus to the selection of surgical candidates or to the specific surgical technique for CM1. We therefore propose a collaborative, prospective, multi-centre study on the investigation, management and outcome of CM1 in the UK.

Objectives

Our primary objective is to determine the patient- or parent-reported, health-related quality of life (HRQoL) in patients with a new diagnosis of CM1 managed either conservatively or surgically at 12 months follow up. This will be measured using the 36-Item Short Form Health Survey (SF-36; UK version) in adults (16 years and above) and the age-appropriate parent-reported Pediatric Quality of Life Inventory™ (PedsQL™ ; UK version) in children (2 to 15 years). We also aim to i) assess the scope and variation of contemporary investigations and neurosurgical management for CM1 in the UK; ii) determine factors that are predictive of postoperative outcome; iii) to examine the outcomes of varying surgical strategies (including HRQoL 12-months following decompressive surgery); and iv) to investigate the natural history of patients managed conservatively.

Methods

The UK Chiari 1 Study will be a prospective, multicentre and observational study that will follow the British Neurosurgical Trainee Research Collaborative (BNTRC) model of collaborative research. Patients will be recruited after attending their first neurosurgical clinic. Afterwards data are collected from all patients undergoing decompressive surgery, other surgery or being treated conservatively for CM1 in participating UK neurosurgical units. Data will be both patient- or parent-reported (via digital questionnaires) and surgeon-reported (via digital questionnaires). Each participating site will complete the study within three years.

3. SYNOPSIS

Study Title	UK Chiari 1 Study		
Internal ref. no. / short title	UK Chiari 1 Study		
Study registration	Oxford PID 269739.		
Sponsor	Oxford University Hospitals NHS Foundation Trust/University of Oxford Research and Development Department, Joint Research Office, Oxford University Hospitals NHS Foundation Trust, [name]; [contact] ; [name]		
Funder	The Ann Conroy Trust; www.annconroytrust.org Chair: [name]; Consultant Neurosurgeon; Department of Neurosurgery, Queen Elizabeth Hospital, Birmingham University Hospitals NHS Foundation Trust; [contact] ; [name]		
Study Design	Prospective, observational, multicentre, cohort study.		
Study Participants	Adults and children referred to neurosurgery clinic for Chiari 1 malformation (CM1)		
Sample Size	500 patients		
Planned Study Period	Total study duration (per site): 36-months Total study duration (for entire study): 42-months Recruitment period duration (per site): 12-months Follow up data for all patients: 12-months following recruitment Additional follow up for patients undergoing decompressive surgery: 12-months following date of decompressive surgery End date (for entire study): 6 th April 2024		
Planned Recruitment period	Participating sites may commence a 12-month recruitment period starting between 8 th October 2020 to 7 th April 2021.		
	Objectives	Outcome Measures	Timepoint(s)
Primary	To determine change in patient- or parent-reported, health-related quality of life (HRQoL) 12 months following first neurosurgical clinic	36-Item Short Form Health Survey (SF-36; UK version) in adults (16 years and above). Age-appropriate parent-reported Pediatric Quality of Life Inventory™ (PedsQL™; UK version) in children (2-15 years).	Baseline and 12-months following baseline
Secondary	To determine health-related quality of life 12-	HRQoL (as per baseline)	Baseline and 12-months following decompressive

	months following decompressive surgery [sub-set of patients undergoing decompressive surgery]		surgery
	To measure complications and need for re-operation 12-months following decompressive surgery [sub-set of patients undergoing decompressive surgery]	Rates of complications and need for further operations following decompressive surgery	12-months following decompressive surgery
	To determine the natural history of patients with CM1 treated conservatively without surgery [sub-set of patients who do not undergo surgery for CM1]	HRQoL (as per baseline)	Baseline and 12-months following baseline
	To determine the radiological correlates of presenting symptoms, signs and outcomes	Measure of cerebellar tonsillar herniation vs. baseline symptoms, baseline HRQoL and follow up HRQoL.	Baseline, 12-months and 12-months after decompressive surgery
Intervention(s)	None. This is an observational study.		

4. ABBREVIATIONS

BNTRC	British Neurosurgical Trainee Research Collaborative
BSCG	British Syringomyelia Chiari Group
CI	Chief Investigator
CM1	Chiari 1 malformation
CRF	Case Report Form
CSF	Cerebrospinal fluid
GCP	Good Clinical Practice
HRQoL	Health-Related Quality of Life
HRA	Health Research Authority
ICF	Informed Consent Form
NHS	National Health Service
NSU	Neurosurgical unit
PedsQL™	Pediatric Quality of Life Inventory™
PI	Principal Investigator
PIL	Participant/ Patient Information Leaflet
R&D	NHS Trust R&D Department
REC	Research Ethics Committee
RES	Research Ethics Service
SBNS	Society of British Neurological Surgeons
SF-36	36-Item Short Form Health Survey
SOP	Standard Operating Procedure

5. BACKGROUND AND RATIONALE

Chiari 1 malformation (CM1) is a structural abnormality of the hindbrain characterised by herniation of the cerebellar tonsils through the foramen magnum. It is one of six described Chiari malformations [1], but is the most common of these and has an estimated prevalence of approximately 8 in 1000 people [2]. CM1 affects patients of all ages, but more commonly presents in late childhood or early adulthood.

CM1 is a heterogeneous condition. Although the natural history is proposed by some to be relatively benign and whilst there are patients who are asymptomatic, CM1 may be accompanied by significant symptoms, deficits and complications [3]. A crowding phenomenon at the foramen magnum manifests as symptoms by causing a combination of brainstem, cerebellar and spinal cord compression. There may be disruption to the normal flow of cerebrospinal fluid (CSF) and around half of imaged patients will have an associated syringomyelia, and a minority of patients develop hydrocephalus [4].

Despite these malformations being classified by Hans Chiari in 1891 [5], CM1 remains poorly understood in aetiology, classification, diagnosis, natural history, investigation and management. There are currently no UK guidelines for the investigation or management of CM1 [6].

Surgery to decompress the cranio-cervical junction (often termed foramen magnum decompression (FMD) remains the mainstay of surgical management, however the surgical technique for decompressive surgery varies widely between centres and surgeons [7, 8] and others would advocate CSF diversion as primary strategy [9]. Common variations of decompressive surgery include bone-only decompression, dura splitting, tonsillar cauterisation, and durotomy with or without duraplasty. Recent single-centre studies from the UK suggest that there may be differences in efficacy and outcomes between these techniques [10, 11], but further evidence is required. The use of intraoperative technologies, such as ultrasonography, to inform surgical decisions also requires further evidence of benefit [12].

Current evidence in CM1 consists of relatively small, single-centre and/or retrospective studies and highly-powered and non-biased data is needed. There are no UK-wide studies that have reported or compared the scope or variability in contemporary neurosurgical workload, practice and outcomes. The lack of evidence in this field makes it difficult for surgeons to decide which patients to offer surgery and which surgical technique is most likely to achieve resolution of symptoms and associated conditions (such as syringomyelia) with minimal complications.

We therefore propose a collaborative, multi-centre and prospective study of the investigation and management of CM1 in the UK.

6. OBJECTIVES AND OUTCOME MEASURES

Objectives	Outcome Measures	Timepoint(s) of evaluation of this outcome measure (if applicable)

Primary Objective
 
To determine change in patient- or parent-reported, health-related quality of life (HRQoL) 12 months following first neurosurgical clinic
	Health-related quality of life (HRQoL) ¹	12-months following baseline

Secondary Objectives
 
[1] To determine health-related quality of life 12-months following decompressive surgery [sub-set of patients undergoing decompressive surgery]
	HRQoL*	12-months following decompressive surgery

[2] To measure complications and need for re-operation 12-months following decompressive surgery [sub-set of patients undergoing decompressive surgery]
	Rates of complications and need for further operations following decompressive surgery	12-months following decompressive surgery

[3] To determine the natural history of patients with CM1 treated conservatively without decompressive surgery
	HRQoL*	Baseline and 12-months following baseline

[4] To determine the radiological correlates of presenting symptoms, signs and outcomes
	Measure of cerebellar tonsillar herniation vs. baseline symptoms, baseline HRQoL* and follow up HRQoL*.	Baseline, 12-months and 12-months after decompressive surgery

Exploratory Objectives
 
To determine the scope and
	Comparison of:	Baseline, 12-months and 12-

¹ Health related quality of life (HRQoL) will be measured in adults (16 years and above) using the 36-Item Short Form Health Survey (SF-36; UK version). HRQoL will be measured in children (2 – 15 years) using the Age-appropriate parent-reported Pediatric Quality of Life Inventory™ (PedsQL™; UK version). Children less than two years of age will be recruited into the study, but not included in the HRQoL analyses.

variation within UK practice in referral patterns, patient pathways, investigations and surgical decisions	
 • Referral pathway • Investigations • Management strategy 	months after decompressive surgery
--	---	------------------------------------

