9.7. Subsequent Assessments

All patients will be followed up at 12-months following first neurosurgical clinic attendance. Patients will be sent an email with a link to the online questionnaire. Either the local study team or steering committee may phone the patient if there is no response to the online questionnaire after seven days.

Surgeon-reported data based on clinical records will also be inputted to the database at the 12-month mark. At the time of this data review, the local investigators will identify a sub-group of the patients who have undergone decompressive surgery since enrolment in the study. For patients who have undergone decompressive surgery, an additional 12-month follow up questionnaire shall be scheduled. Similarly, this sub-group of patients will be sent an email with a link to their questionnaire 12-months after their

operation and the study team or steering group may follow up with a phone call, if necessary, after seven days.

For each follow up timepoint, patient-reported data (i.e. questionnaires) must be completed within 45-days from the target date to be included in the analysis).

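### The natural-history group (secondary objective 3) is defined differently in the synopsis and section 6, and both wordings fix membership by surgery during the 12-month outcome window

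*Protocol*

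**What the plan says.** The protocol describes the natural-history group in two places, and the descriptions differ.

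- **Synopsis (section 3):** the group is the "sub-set of patients who do not undergo surgery for CM1". Any operation for CM1 removes a patient.
- **Section 6, secondary objective [3]:** "To determine the natural history of patients with CM1 treated conservatively without decompressive surgery". The only operation named is decompression, and no subset is given in brackets.

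Other sections bear on how the group would be formed in practice.

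- **Lay summary (section 2), Methods:** data come from patients having "decompressive surgery, other surgery or being treated conservatively for CM1". This lists three kinds of management, with other surgery separate from conservative care.
- **Background (section 5):** non-decompressive surgery is a recognised first treatment, since "others would advocate CSF diversion as primary strategy".
- **Section 7:** length of follow-up depends only on whether the patient has decompressive surgery.
- **Section 9.7:** surgical status is established at the 12-month record review, when "the local investigators will identify a sub-group of the patients who have undergone decompressive surgery since enrolment in the study".
- **Section 11.1** states that no separate SAP is in use. **Section 11.2** covers the primary outcome, the decompression subgroup and the exploratory objective, but gives no rule for objective 3.

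**The concern.** There are two problems.

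First, the two wordings disagree about a real category of patient. Someone treated by CSF diversion is out under the synopsis, but is not removed by the surgical criterion in section 6. The study's own procedures separate only decompressed from non-decompressed patients, so a default split would put these patients with the unoperated. If the choice is left until results are available, it can be influenced by them.

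Second, under either wording membership is settled by what happens during the outcome window. A patient managed conservatively at first and operated on before month 12 leaves the group. A patient whose operation falls after month 12 stays in. If worsening makes surgery more likely, the group loses its worse courses, and its 12-month change overstates how well initially conservative patients fare. The background section says that some regard the natural history as fairly benign. A bias in this direction would therefore favour one answer to the question the objective asks.

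**Working it through.** **Step 1: classify each type of patient under each wording.**

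| Course over 12 months | Synopsis | Section 6 (surgical criterion) | Split in 7 and 9.7 |
|---|---|---|---|
| No CM1 surgery | in | in | not decompressed |
| CSF diversion or other CM1 surgery only | out | not excluded | not decompressed |
| Conservative at first, decompressed before month 12 | out | out | decompressed |
| Surgery only after month 12 | in, if judged at month 12 | in, if judged at month 12 | not decompressed at the review |

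The second row is the conflict between the definitions. The third and fourth rows show that membership depends on later events. Neither observation needs arithmetic.

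**Step 2: illustrate the selection effect.** The protocol gives no figure for this group, so there is none to reproduce. The inputs below are all assumptions:

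- SD of the 12-month change: 20 points
- share *c* of initially conservative patients operated on before month 12: 10%, 20% or 30%
- correlation *r* between untreated decline and having surgery: 0, 0.3 or 0.5

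Let tendency to surgery and untreated change be jointly normal, with the *c* highest on the tendency being operated on. The upward shift in the retained group's mean change is then

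shift = SD × *r* × φ(z) / (1 − *c*), where z is the (1 − *c*) normal quantile.

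In SD units, r × φ(z)/(1 − c), then multiplied by 20:

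| *c* | *r* = 0 | *r* = 0.3 | *r* = 0.5 |
|---|---|---|---|
| 10% | 0 | 0.058 SD → 1.2 points | 0.097 SD → 1.9 to 2.0 points |
| 20% | 0 | 0.105 SD → 2.1 points | 0.175 SD → 3.5 points |
| 30% | 0 | 0.149 SD → 3.0 points | 0.248 SD → 5.0 points |

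A simulation of 1,000,000 patients agreed with the formula to within 0.001 SD. At *r* = 0.7, the shift at *c* = 30% is 0.348 SD.

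**Step 3: illustrate the mixing effect.** If other-surgery patients form a share *s* of the group and their change differs by *e* SD, the group mean moves by *s* × *e*. With *s* from 2% to 15% and *e* from 0.3 to 0.8 (both assumed), this is 0.02 × 0.3 = 0.006 SD up to 0.15 × 0.8 = 0.12 SD. At SD 20 that is 0.12 to 2.4 points.

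**The case against.** **Section 6 already says treated conservatively.** Because the lay summary lists other surgery apart from conservative care, a CSF-diversion patient may not be conservative in the protocol's own vocabulary. This is a fair reading, and it means such patients may be counted, not that they will be. It does not remove the conflict: section 6 then qualifies the phrase by decompression alone, and no analysis rule decides the matter.

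**No passage says that deterioration leads to surgery.** This is correct. Operations in the first year may carry out a plan made at first clinic. Those patients were never conservative, and removing them is right. If surgery is unrelated to decline, the shift is zero. The bias is therefore conditional, but the plan offers nothing that would show whether it is present.

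**Patients still waiting for surgery at month 12 are untreated, so their course is natural history.** This also stands. If they are worsening, keeping them may offset part of the shift.

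**Grouping by initial decision answers a different question.** It describes the outcome of an initial strategy and includes some scores measured after an operation. No HRQoL assessment is scheduled just before surgery, so the two cannot be separated. This is why that group should accompany the never-operated subset and not replace it.

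**A stronger reading to avoid.** A reader might infer that the lay summary contradicts section 11.2, since it states the primary objective for HRQoL "in patients with a new diagnosis of CM1 managed either conservatively or surgically at 12 months follow up" while 11.2 pools all patients. The phrase reads naturally as describing who is included, however managed. That agrees with the synopsis, section 6 and section 11.2, none of which stratifies the primary objective. A reader might also infer that mixing in CSF diversion leaves no natural-history result at all. Even on the assumed inputs, the effect in Step 3 is at most 0.12 SD.

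**Conclusion.** The inconsistency is established from the text: the synopsis and section 6 define the group differently, the procedures follow the looser split, and section 11 does not settle it. It is also established that membership under both wordings depends on surgery during the outcome window.

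The size of any resulting bias cannot be derived from the documents. With SD 20, 10–30% crossing and correlation 0–0.5, it lies between 0 and about 5 points. The SD, crossing share and correlation are all assumed. One SD is used for both instruments, although section 11.4 analyses SF-36 and PedsQL separately. The direction, towards a more benign picture, holds only if worsening patients are more likely to be operated on.

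This is a secondary-objective issue. It affects objective 3 and the matching natural-history aim in the lay summary. The primary analysis covers all patients and is untouched, and section 11.2 plans no comparison of conservative with surgical management that would inherit the problem.

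**What to change.** 1. Use one definition of the natural-history group in the synopsis, section 6 and section 11.2: no CM1 surgery of any kind up to the 12-month assessment. Make other CM1 surgery its own category, and have the 12-month record review in section 9.7 identify it alongside decompression.
2. In section 11.2, state that the 12-month HRQoL change will be reported for two groups:
   - all patients whose recorded management decision at first clinic was conservative, with the number and timing of later operations, split into decompression and other CM1 surgery;
   - the never-operated subset, with a statement that it is selected on later events.
3. Settle this before the outcome data are analysed.

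The cost is protocol wording and one grouping variable. There are two caveats. The initially conservative group will contain some 12-month scores obtained after surgery; the count and timing of operations show how many. The sponsor must also confirm that the first-clinic decision is a recorded field. Section 6 lists management strategy as an exploratory item with a baseline timepoint, but the list of data fields is not in the supplied text. If the decision is not recorded, it would have to be taken from the clinic records.

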11. STATISTICS AND ANALYSIS

11.1. Statistical Analysis Plan (SAP)

The plan for the statistical analysis of the study are outlined below. There is not a separate SAP document in use for the study.

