11.2. Description of the Statistical Methods

For the primary outcome, the baseline and 12-month HRQoL assessments will be used for analysis. For all patients, comparison will be made between baseline and 12-months, but both will also be compared against the UK normative datasets.

For the secondary outcome pertaining to the sub-group undergoing decompressive surgery, HRQoL data will be similarly be compared to baseline and to UK normative datasets. Further comparisons of outcome data will be made between specific surgical techniques used, baseline symptoms and radiological findings.

Descriptive statistics will be used to report the data from the exploratory objective, regarding referral pathways, investigations and management strategies for CM1 in UK neurosurgical practice.

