11.3. Sample Size Determination

A pilot retrospective data review from two neurosurgical units (Birmingham and Oxford) showed that, in one month, one unit saw eleven and the other saw four patients that met the inclusion criteria aforementioned. Assuming a 50% recruitment rate, we would recruit around 90 patients in one year in these two units. Although we hope that more than 30 NSUs take part, if 12 similar sized units took part, we could potentially recruit >500 patients. These pessimistic estimates will account for some NSUs not taking part and also for patient withdrawals.

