18. PUBLICATION POLICY

In publications of national data, as per the BNTRC model (Chari et al., 2018), all participating trainees and consultants will be named as PubMed-citable collaborators. The REDCap database allows visibility of data input and will ensure that named collaborators have contributed towards the study. Authorship will be decided in accordance with the *International Committee of Medical Journal Editors* (ICMJE). Authors thus far will include the steering group of the UK Chiari 1 Study ([name], [name], [name], [name], [name], [name] & [name]), the BSCG and the BNTRC. As per the BNTRC constitution, the senior author will be the BNTRC (<https://www.bntrc.org.uk/about-us>).

The steering committee and BNTRC will retain ownership of the entire national dataset and the right to publish the data. Local data, however, will be available to the local investigators to facilitate local audit. Local outputs must acknowledge the *UK Chiari 1 Study*.

We plan to submit the following reports for both presentation at national/international meetings and peer-reviewed publication:

- The study protocol, as exemplified by the *BNTRC UK Cranioplasty Registry* (Koliass et al., 2014) and the *Understanding Cauda Equina Study* (Woodfield et al., 2018)
- *UK Chiari 1 Study* outcomes

This study is intended as a research study in order to inform further research and perhaps future clinical practice. Variance in practice or the outcomes of individual NSU or neurosurgeon will be available for each NSU to review, but NSU or individual neurosurgeon identifying data will not be exposed publicly or to any other NSU.

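### Variation in UK practice is an exploratory objective, but the only method named for it is descriptive statistics, and raw unit proportions cannot separate practice from chance and case-mix

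*Protocol*

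**What the plan says.** Section 6 lists, under exploratory objectives, the scope and "variation within UK practice in referral patterns, patient pathways, investigations and surgical decisions". The measure is a comparison of referral pathway, investigations and management strategy. The lay summary (section 2) gives a related aim, to "assess the scope and variation of contemporary investigations and neurosurgical management for CM1 in the UK", and says where the variation is thought to lie: "Practice varies widely between neurosurgical units and individual surgeons".

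For the method, section 11.2 states: "Descriptive statistics will be used to report the data from the exploratory objective". Section 11.1 adds: "There is not a separate SAP document in use for the study". Section 11 mentions no interval, unit-level model or case-mix adjustment for this objective.

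Section 18 describes one use of the results: "Variance in practice or the outcomes of individual NSU or neurosurgeon will be available for each NSU to review". It also limits that use, since unit or "individual neurosurgeon identifying data will not be exposed publicly or to any other NSU".

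**The concern.** The objective has two halves. Scope asks which pathways, investigations and operations are used in the UK, and how often. Variation asks how far practice differs, and the lay summary places that difference between units and surgeons. A table answers the first half. For the second, a raw unit proportion mixes three things: how the unit decides, sampling error in a small number of patients, and the kind of patients the unit sees.

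The last two are not small here. Section 11.3 implies a few dozen patients per unit. Entry runs from 0 days of age with no upper limit (8.1) and sets no herniation threshold (8.2), and section 5 calls the condition heterogeneous, with some patients asymptomatic. Units that decide alike could therefore show visibly different rates. If the figures returned to units under section 18 are unadjusted and carry no measure of uncertainty, a unit could take noise for a feature of its own practice. Figures for individual surgeons would rest on fewer patients still.

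**Working it through.** **The protocol's own forecast (section 11.3).** The pilot found that "in one month, one unit saw eleven and the other saw four patients that met the inclusion criteria aforementioned". With 12 months and 50% recruitment:

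- larger unit: 11 × 12 × 0.5 = 66 patients;
- smaller unit: 4 × 12 × 0.5 = 24 patients;
- both: 66 + 24 = 90, as stated;
- 12 similar units: (90 / 2) × 12 = 540, in line with the stated figure of more than 500.

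**Precision for one unit.** The 95% half-width of a proportion is 1.96 × √(p(1 − p)/n). At an assumed p = 0.30:

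- n = 66: 1.96 × √(0.21/66) = 0.11, or 11 points;
- n = 24: 1.96 × √(0.21/24) = 0.18, or 18 points.

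**Spread from chance alone.** Take six units of 66 and six of 24 (6 × 66 + 6 × 24 = 540), give all of them the same true operation rate, draw binomial counts, and record the lowest and highest observed rate. The protocol gives no operation rate, so 20% to 50% is an assumed range. Results from 50,000 replicates (the last column from a separate run of 40,000):

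| True rate in every unit | Mean lowest | Mean highest | Mean gap | 5th–95th percentile of gap | Gap of 20 points or more |
|---|---|---|---|---|---|
| 20% | 9% | 32% | 22 points | 13–33 | 66% |
| 30% | 18% | 43% | 26 points | 16–38 | 81% |
| 50% | 36% | 64% | 28 points | 17–42 | 88% |

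The result does not depend on the mix of large and small units. Twelve equal units of 42 (500/12) run on average from 19% to 42% at a true 30%. If about 30 units share 500 patients (about 17 each), in the direction section 11.3 hopes for, the range widens to 9% to 54%.

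**Surgical technique.** Only operated patients count. With 42 patients per unit and 20%, 30% or 50% operated, a unit has about 8, 13 or 21 operated patients. If every unit truly uses a given technique in half its operations, the mean gap across 12 units is 56, 44 or 35 points.

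**Case-mix, as an illustration with assumed figures.** Suppose every unit operates on 60% of patients with syringomyelia and 15% of those without. A unit with 30% syringomyelia shows 0.3 × 0.60 + 0.7 × 0.15 = 28.5%. A unit with 70% shows 0.7 × 0.60 + 0.3 × 0.15 = 46.5%. The gap is 18 points with identical decisions.

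**The case against.** The strongest reply is that this is an ordinary choice for an exploratory objective with no hypothesis. Observed patterns are commonly described rather than modelled, and variation within UK practice need not mean variance between units. If every unit used duraplasty in half its operations, practice would still vary, and a national frequency table would show it. This stands for scope and for the national mix. It would be wrong to infer that the objective cannot be answered at all by the stated method.

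Two other stronger readings are also unsupported. A reader might infer that the plan restricts the analysis to descriptive statistics. Section 11.2 says what will be used and excludes nothing; intervals and stratified tables would be compatible with it. A reader might also infer that the study will report chance differences as true differences in practice. No section says that raw unit ranges will be ranked or read in that way, and section 18 keeps identifying unit and surgeon results from the public and from other units.

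It is also fair that the lowest-to-highest range is the summary most sensitive to chance, that the protocol does not promise to report it, and that the operation rates are assumed. The table therefore shows how noisy unit results would be; it does not predict what the report will say.

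What remains is that the lay summary and section 18 do bring in the unit and surgeon level, that no other method is named for this objective, and that the protocol rules out a separate SAP to supply one.

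**Conclusion.** The concern holds in limited form. For the between-unit part of the objective, the one method named cannot distinguish practice differences from chance and case-mix, and at the forecast unit sizes chance alone produces average gaps of 22 to 28 points between the lowest and highest of 12 identical units. This rests on assumed true rates of 20% to 50% and on pilot-like unit sizes; the conclusion is the same across that range and with equal units. The size of any case-mix effect is not known from the document.

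The severity is minor. The objective is exploratory, the primary and secondary analyses are unaffected, and the protocol contains no contradiction on this point. It is a cheap improvement.

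**What to change.** In section 11.2, keep the descriptive tables and add:

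1. Unit-level results are given with denominators and 95% intervals, or against funnel-plot limits, with adults and children shown separately. The same applies to results returned to units under section 18.
2. For the common binary decisions (operated or not, key investigation done or not), a logistic model with a random intercept for neurosurgical unit is fitted, adjusted for adult or child and a few baseline severity variables. Baseline symptoms and tonsillar herniation are natural choices, since secondary objective 4 already needs them. The between-unit variance or median odds ratio is reported with its interval.
3. Surgical technique stays descriptive, because operated patients per unit are few, with a statement that differences between units are unadjusted and may reflect chance and case-mix.

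No rule is needed that variation may be claimed only where it exceeds chance; with few units, such a rule could hide real differences.

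The cost is a few sentences and a small number of models on data already collected. The downside is that with about 12 units the between-unit variance will have a wide interval, which should be reported as it stands.
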